5.3 Investigator and Institutional Requirements

Principle investigator and co-investigators comply with institutional research procedures and policies. The study will be activated after approval by the IRB.

5.4 Study Calendar (Accrual process)

Visits	Activities	Site/Person involved
Initial clinic visit	Determination of eligibility	GU multidisciplinary center
Imaging visit	Standard of care Bone scan	Diagnostic Imaging
Imaging visit	The standard of care CT abdomen	Diagnostic Imaging
Imaging visit	The standard of care pelvic MRI with endorectal coil	Diagnostic Imaging
Imaging visit	Research 18F-fluciclovine PET CT	Diagnostic Imaging

5.5 Pre-test/study evaluation

Patients with metastatic prostate cancer are seen and evaluated at genitourinary multidisciplinary care center of MDACC. Based on the past clinical volumes, we are expected to see 2-4 metastatic prostate cancer patients per month. This center is staffed by clinical faculty from urology, medical oncology, and radiation oncology departments. Before enrollment, patients will be seen in genitourinary multidisciplinary center in consultation with a medical oncologist, urologist, and radiation oncologist to ensure eligibility.

5.6 Registration Visit and Procedures

Verification of eligibility criteria, and clinical consultation notes by DI research nurse. All patients will be scheduled to undergo standard of care laboratory studies and imaging workup that include PSA, bone scan, CT abdomen and mpPelvic MRI with the endorectal coil. Informed consent will be obtained by either by a qualified research personnel or research staff.

5.7 Baseline Imaging Visits

Baseline bone scan, CT abdomen, mpPelvic MRI (or) 18F-fluciclovine PET CT will be scheduled or completed within 30 days before initiation of SST. Please refer to Appendix C. for complete imaging protocols.

5.8 Post Systemic Therapy-Imaging Visits

Patients will return following 22-28 weeks (+/- 4 weeks) of SST for follow-up imaging studies which will include MDP Bone scan, CT abdomen, MP PELVIC MRI AND 18F-FLUCICLOVINE PET CT.

5.9 Criteria for Removal from Study

Subjects must be withdrawn from the study for the following reasons:

- 5.9.1 The patient withdraws consent
- 5.9.2 The patient cannot complete all imaging tests within 30 days of time frame.
- 5.9.3 Study completed

5.10 Innovation:

This is to our knowledge the first study of using 18F-fluciclovine PET CT in the assessment of therapy response in prostate cancer. Although glucose metabolism is recognized as a key metabolic pathway for imaging, amino acid metabolism is emerging as a promising pathway for

tumor imaging.^{30,31} Recent studies with ¹⁸F-Fluciclovinehave shown that this tracer can accurately detect prostate cancer and regional lymph node metastases with better specificity and sensitivity.³²⁻ ³⁴ 18F-fluciclovine have also been tried in breast cancer with positive results. A pilot study evaluated the ability of ¹⁸F-fluciclovine avidity to determine neoadjuvant therapy response in 24 breast cancer patients, using histology after definitive surgical management as the gold standard.³⁵ Changes in ¹⁸F-fluciclovine avidity strongly correlated with the percentage of reduction of tumor seen on pathology.³⁵ Motivated by these prior studies, we propose to evaluate the ability of 18F-fluciclovine avidity to determine neoadjuvant therapy response in M1PCa. In addition to establishing the importance of tumor response assessment with novel radio tracers, this study has the potential to combine with pelvic MRI and whole-body MRI to study high risk and metastatic prostate cancer. Also, the knowledge gained from this research will be used to design and test the utility of PET-MRI with novel tracers such as 18F-fluciclovine and PSMA. The culmination of the pilot studies will be an extramural application to conduct a multicenter trial.

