1.0 PROTOCOL OVERVIEW (SCHEMA)

Eligible metastatic prostate cancer patients >/= M1a (castration naïve)

PSA Testing, Bone scan, CT abdomen, Pelvic MRI

Baseline 18F FluciclovinePETCT before initiation of SST

22-28 weeks of SST

PSA Testing, Bone scan, CT abdomen, Pelvic MRI

Repeat 18F FluciclovinePETCT

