5.0 Research Design and Methods

5.1 Study Design

A prospective pilot study will consist of eligible patients referred from genitourinary multidisciplinary care center at the University of Texas at MD Anderson cancer Center. All eligible patients scheduled to receive SST for up to 28 weeks will be enrolled, and initial 18F-fluciclovine PET CT will be performed within four weeks before initiation of systemic therapy. The patient will receive SST for up to 28 weeks, and 18F-fluciclovine PET CT will be repeated within four weeks following SST. 18F-fluciclovine PET CT will be performed as per the standard institutional protocol (Appendix C.). Blinded image interpretation will be made by radiologists and nuclear medicine physician. All scans will be interpreted independently by two physicians. Areas of focal tracer uptake will be localized with the companion CT and classified as lesions of the prostate, pelvic nodes, extrapelvic nodes, visceral, and bone lesions. Three- dimensional regions of interest will be placed in areas of tracer uptake, and measures of 18F- fluciclovine avidity will be recorded; the measures include SUVmax (body weight), metabolic tumor volume (MTV; volume of tumor [cm3] with SUV >42% of SUVmax), SUVmean (within the MTV), and total lesion avidity (TLA; calculated as MTV x SUVmean). A background SUVmax will be documented for each examination. On both pretreatment and posttreatment scans, the lesion SUVmax will be corrected for the background as follows: corrected SUVmax = lesion SUVmax background SUVmax. When the correct SUVmax is less than 0, 0 will be recorded. Similar corrections will be made for SUVmean. When the corrected SUVmax and the corrected SUVmean are 0 on posttreatment scans, MTV and TLA will also be recorded as 0. The percentage of change in the 18Ffluciclovine SUVmax after therapy will be calculated as follows: [(pretreatment corrected SUVmax posttreatment corrected SUVmax)/pretreatment corrected SUVmax] x 100. Similar calculations will be performed for SUVmean, MTV, and TLA.

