6.0 Statistical Considerations

Objectives, Endpoints, and Study Design

The primary objective of this prospective study is to evaluate the ability of 18F Fluciclovine PET CT to determine the therapeutic response to SST. All eligible patients will be imaged by 18F Fluciclovine PET CT before and after treatment. Treatment responders were defined as the posttreatment PSA level <= 4.0 ng/mL, and >4.0 ng/mL for non-responders. The primary endpoint is the percentage change of 18F-fluciclovine SUVmax. Secondary endpoints include the size changes defined by conventional imaging; TBR; sensitivity, specificity, positive predictive value (PPV), and negative predictive value (NPV) when comparing 18 F Fluciclovine PET CT imaging findings with pathologic findings; progression free survival defined by PCWG2 criteria; and the types of metastatic progression sites. The accuracy of using the percentage change of 18F- Fluciclovine SUVmax to discriminate treatment responders from non-responders is evaluated using Receiver Operating Characteristic (ROC) curve analysis.

Sample Size and Power Calculation

We wish to enroll 41 evaluable patients. With an overall sample size of 41 and an estimated 70% response rate, we expect approximately 28 responders and 13 non-responders. With these numbers, we will have 83% power to detect a difference of 0.26 between the area under the ROC curve (AUC) under the null hypothesis of 0.50 and an AUC under the alternative hypothesis of 0.76 using a two-sided z-test at a significance level of 0.05. Considering a drop-out rate of 10%, the total sample size required is 45.

Analysis Plan

Patient characteristics and clinical outcomes will be summarized using frequencies, mean, standard deviation, median, and range. Accuracy of predicting responders using the percentage changes of SUVmax or the size changes by conventional imaging will be analyzed by ROC curves. AUC will be compared using the nonparametric method described by Delong (1988). Optimal cut- off points for dichotomizing the percentage changes of SUVmax or the size changes will be selected by maximizing the Youden's index. Dichotomized values will be compared using the McNemar's test. Sensitivity, specificity, PPV, and NPV to correlate dichotomized 18 F Fluciclovine PET CT imaging findings with pathologic findings will be estimated along with 95% confidence intervals.

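### The listed conventional scans give no stated source of size measurement for soft-tissue disease above the diaphragm, so SUVmax change and size change may be compared over different lesions

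*Combined protocol and SAP*

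**What the plan says.** **Scans.** The schema in Section 1.0 lists "PSA Testing, Bone scan, CT abdomen, Pelvic MRI" both before and after systemic therapy. Section 5.6 describes an "imaging workup that include PSA, bone scan, CT abdomen and mpPelvic MRI with the endorectal coil". The calendar in Section 5.4 has "The standard of care CT abdomen" as its only conventional CT. Section 5.7 gives the same set at baseline and adds "Please refer to Appendix C. for complete imaging protocols". Section 5.8 describes "follow-up imaging studies which will include MDP Bone scan, CT abdomen, MP PELVIC MRI AND 18F-FLUCICLOVINE PET CT". None of these names cross-sectional imaging of the chest.

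**Patients.** The schema admits "Eligible metastatic prostate cancer patients >/= M1a". Section 4.2 excludes only known brain metastasis and small cell carcinoma, so thoracic or supraclavicular nodes and lung lesions do not bar entry.

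**Measurements.** Section 5.2 applies RECIST 1.1 to visceral, bone and nodal metastases. Section 5.1 has areas of PET uptake "classified as lesions of the prostate, pelvic nodes, extrapelvic nodes, visceral, and bone lesions". It uses the companion CT to localise uptake and does not assign it to measuring diameters.

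**Analysis.** Size change by conventional imaging is part of the primary objective's correlation (Section 3.0) and a secondary endpoint (Section 6.0). Section 6.0 also states that "size changes by conventional imaging will be analyzed by ROC curves", as for SUVmax change. AUCs are then compared by DeLong's method and dichotomised values by McNemar's test.

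**The concern.** A paired comparison of two markers is easiest to interpret when both describe the same disease in the same men. Here PET may record an avid mediastinal or supraclavicular node or a lung lesion, provided its field includes the chest. The listed conventional scans provide no diameter for that lesion. The bone scan extends beyond the abdomen and pelvis but does not size soft tissue.

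In a man with such disease, SUVmax change may draw on lesions that size change leaves out. Size change could then discriminate PSA responders less well for a reason unrelated to the merit of size as a marker, and the error would favour PET. Section 5.10 presents the pilot as groundwork for a multicentre application, so a coverage artefact could be carried forward as evidence for the tracer.

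Objective 3 has a related gap. It separates progression at initial sites from progression at new ones, but the plan does not say which baseline imaging defines an initial site.

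**Working it through.** **1. The plan's own figure.** Inputs from Section 6.0: 28 responders, 13 non-responders, AUC 0.50 against 0.76, two-sided 0.05. The Hanley-McNeil variance is

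V(A) = [A(1−A) + (n₁−1)(Q₁−A²) + (n₀−1)(Q₂−A²)] / (n₁n₀), with Q₁ = A/(2−A) and Q₂ = 2A²/(1+A).

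- A = 0.50: V = (0.25 + 27×0.0833 + 12×0.0833)/364 = 3.5/364, so SE₀ = 0.0981.
- A = 0.76: V = (0.1824 + 27×0.0353 + 12×0.0788)/364, so SE₁ = 0.0756.
- Power = Φ[(0.26 − 1.96×0.0981)/0.0756] = Φ(0.897) = 81.5%.

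The binormal Obuchowski-McClish variance gives 81.3%. Both are within 2 points of the stated 83%. No input depends on which body regions the conventional scans cover, so this point does not change the figure.

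**2. Number of men affected.** The documents do not give the share f with soft-tissue disease above the diaphragm. Assuming 5% to 20%: 0.05×41 = 2.1 and 0.20×41 = 8.2, or about 2 to 8 of the 41 evaluable men.

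**3. Possible bias (illustration).** Suppose size change has a true AUC of 0.76 but carries no information in a share f of each response group. The loss depends on how those men's size values are recorded.

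- If they all fall at one extreme of the scale, any responder/non-responder pair with an affected man counts 0.5 on average: AUC = 0.5 + 0.26(1−f)².
- If they look like random draws from all the men, a pair with one affected man averages (0.76 + 0.50)/2 = 0.63, and a pair with two averages 0.5: AUC = 0.76(1−f)² + 2f(1−f)×0.63 + 0.5f² = 0.5 + 0.26(1−f).

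| f (assumed) | Extreme values: AUC (gap from 0.76) | Random draws: AUC (gap) |
|---|---|---|
| 5% | 0.735 (0.025) | 0.747 (0.013) |
| 10% | 0.711 (0.049) | 0.734 (0.026) |
| 20% | 0.666 (0.094) | 0.708 (0.052) |
| 30% | 0.627 (0.133) | 0.682 (0.078) |

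Both columns assume that size is wholly uninformative in affected men. A man who also has measurable abdominal, pelvic or prostatic disease keeps some information, and the gap shrinks.

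**4. Possible loss of precision.** If 8 men are left out of the size analysis at random (about 23 and 10 remain), SE at 0.76 is √[(0.1824 + 22×0.0353 + 9×0.0788)/230] = 0.085, against 0.0756. This is the standard error of one AUC. It does not measure bias, and it is not the standard error of the paired DeLong difference.

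**The case against.** A reader might infer that disease above the diaphragm is never sized. The documents do not support that. Sections 5.6 and 5.8 introduce their lists with forms of the verb include, Section 4.1 does not restrict eligibility CT to the abdomen, and Section 5.7 refers to Appendix C, whose text is not available here. What stands is that no source of size measurement is stated. Chest CT obtained in some men without a rule would not cure this, because coverage would then vary from man to man.

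A reader might infer that a new chest lesion cannot count as progression. Section 5.2 counts any new lesion and sets no limit on modality.

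A reader might also infer that objective 3 will mislabel sites as new. That is not shown. Baseline PET/CT records avid extrapelvic nodal and visceral lesions, and nothing restricts initial sites to conventional imaging. The risk is confined to non-avid disease or to a site rule that ignores PET.

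Other limits also stand. M1a does not imply disease above the diaphragm, since retroperitoneal nodes would fall within CT abdomen. The PET field is not stated in the available text. The plan does not say which lesion supplies a man's SUVmax. Nothing in the documents shows that affected men would mostly be non-responders.

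**Conclusion.** The point holds as a conditional weakness in the size comparator. As written, the DeLong and McNemar comparisons of SUVmax with size can span different body regions, and the resulting error would favour PET. The primary objective's correlation with size change is exposed in the same way.

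The size is unknown because f is not given. At an assumed 5% to 20%, with size wholly uninformative in those men, the spurious AUC gap is about 0.013 to 0.094. It would be smaller where affected men also have measurable disease in the field, and zero if no such men enrol. The conclusion assumes that the PET field includes the chest and that Appendix C supplies no chest measurement.

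A reader might infer that the main result is compromised. It is not: the responder label is PSA, and the primary SUVmax AUC test and its 83% power do not use conventional imaging. The change should be made because it needs no new scan and removes an explanation that would be hard to exclude afterwards.

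**What to change.** 1. **Section 6.0:** repeat the SUVmax-versus-size AUC and McNemar comparisons using only lesions within the field shared by PET and the conventional scans. A difference that persists there cannot be put down to coverage.
2. **Section 6.0, separately reported sensitivity analysis:** add diameters of out-of-field lesions, measured on the companion CT of each PET/CT at both time points, by readers blinded to tracer uptake where feasible.
3. **Objective 3:** call a site prior if it was positive on baseline conventional imaging or on baseline PET/CT.

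**Cost:** some extra measurement and analysis. Section 10.0 already budgets PET/CT at two time points per man. The companion CT may be less precise for small nodes. Diameters taken from it also depend partly on the index test, because tracer uptake could steer which lesions are measured, so they stay out of the main comparison.

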5.11 End of the Study information handling

All collected information from participants will be destroyed, including patient identifiers. This information will be destroyed within 5 years from publication in accordance with UT MD Anderson Cancer Center policies.

6.0 Statistical Considerations

Objectives, Endpoints, and Study Design

The primary objective of this prospective study is to evaluate the ability of 18F Fluciclovine PET CT to determine the therapeutic response to SST. All eligible patients will be imaged by 18F Fluciclovine PET CT before and after treatment. Treatment responders were defined as the posttreatment PSA level <= 4.0 ng/mL, and >4.0 ng/mL for non-responders. The primary endpoint is the percentage change of 18F-fluciclovine SUVmax. Secondary endpoints include the size changes defined by conventional imaging; TBR; sensitivity, specificity, positive predictive value (PPV), and negative predictive value (NPV) when comparing 18 F Fluciclovine PET CT imaging findings with pathologic findings; progression free survival defined by PCWG2 criteria; and the types of metastatic progression sites. The accuracy of using the percentage change of 18F- Fluciclovine SUVmax to discriminate treatment responders from non-responders is evaluated using Receiver Operating Characteristic (ROC) curve analysis.

Sample Size and Power Calculation

We wish to enroll 41 evaluable patients. With an overall sample size of 41 and an estimated 70% response rate, we expect approximately 28 responders and 13 non-responders. With these numbers, we will have 83% power to detect a difference of 0.26 between the area under the ROC curve (AUC) under the null hypothesis of 0.50 and an AUC under the alternative hypothesis of 0.76 using a two-sided z-test at a significance level of 0.05. Considering a drop-out rate of 10%, the total sample size required is 45.

Analysis Plan

Patient characteristics and clinical outcomes will be summarized using frequencies, mean, standard deviation, median, and range. Accuracy of predicting responders using the percentage changes of SUVmax or the size changes by conventional imaging will be analyzed by ROC curves. AUC will be compared using the nonparametric method described by Delong (1988). Optimal cut- off points for dichotomizing the percentage changes of SUVmax or the size changes will be selected by maximizing the Youden's index. Dichotomized values will be compared using the McNemar's test. Sensitivity, specificity, PPV, and NPV to correlate dichotomized 18 F Fluciclovine PET CT imaging findings with pathologic findings will be estimated along with 95% confidence intervals.

Kaplan-Meier method will be used to estimate progression free survival (PFS). Log-rank test will be used to compare PFS between imaging response groups. Frequencies will be estimated for different types of metastatic progression sites. Other statistical analyses will be carried out as appropriate.

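### Do the stated inputs fail to give 83% power, and is the powered test missing from the plan?

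*Combined protocol and SAP*

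**What the plan says.** All the relevant text is in section 6.0, Statistical Considerations, of the combined protocol and SAP.

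- **Objectives, Endpoints, and Study Design** makes the percentage change in SUVmax the primary endpoint. Its ability to separate PSA responders from non-responders is to be judged by ROC analysis. Size change on conventional imaging is listed as a secondary endpoint.
- **Sample Size and Power Calculation** begins "We wish to enroll 41 evaluable patients" and continues "With an overall sample size of 41 and an estimated 70% response rate, we expect approximately 28 responders and 13 non-responders". On those numbers it claims that "we will have 83% power to detect a difference of 0.26". The AUC is 0.50 under the null and 0.76 under the alternative, and the comparison is made "using a two-sided z-test at a significance level of 0.05". The paragraph ends "Considering a drop-out rate of 10%, the total sample size required is 45".
- **Analysis Plan** applies ROC curves to SUVmax change and to size change, and then says "AUC will be compared using the nonparametric method described by Delong (1988"). It does not say which AUCs are compared, and it does not repeat the test against 0.50.

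**The concern.** Three things look wrong.

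1. The split of 28 and 13 is not 70% of 41 to the nearest patient, and the rounding enlarges the smaller group, which limits the power.
2. Enrolling 45 with 10% lost leaves 40.5 evaluable patients, not 41.
3. Power is computed for one AUC against 0.50, whereas the only AUC test named under Analysis Plan is DeLong's. Coming straight after two predictors, it most naturally means SUVmax change against size change, and that comparison has no power statement.

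If the true power were well below 83%, the pilot would be over-promised. If the powered test were absent, the primary analysis would be open to choice after the data are seen, and a reader might attach the 83% to the comparison of PET with conventional imaging.

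**Working it through.** **Inputs, all from section 6.0.** AUC 0.50 under the null and 0.76 under the alternative; two-sided alpha 0.05; 28 responders and 13 non-responders; 41 evaluable; 70% response; 10% drop-out; 45 enrolled. The plan names no variance formula. I assume a binormal model with equal standard deviations in the two groups.

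**Formula.** Power = Φ((0.26 − 1.96·SE0)/SE1), where SE0 is the standard error at AUC 0.50 and SE1 that at 0.76. With group sizes m and n, and a = √2·Φ⁻¹(AUC):

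Var = f²[(1 + a²/2)/m + 1/n] + (g²/2)(1/m + 1/n) + f·g·a/m

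where f = exp(−a²/4)/√(4π) and g = −a·f/2.

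**The plan's own figure, m = 28, n = 13**

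- Null: a = 0, f² = 0.0796, g = 0. Var = 0.0796 × (1/28 + 1/13) = 0.00896, so SE0 = 0.0947.
- Alternative: a = 0.9989, f = 0.2198, g = −0.1098. Var = 0.00630 + 0.00068 − 0.00086 = 0.00612, so SE1 = 0.0782.
- Power = Φ((0.26 − 0.1856)/0.0782) = Φ(0.951) = 82.9%. This agrees with the stated 83%.

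Other standard choices at 28/13 with responders as the positive group fall close by. Hanley-McNeil has SE0 = 0.0981 and SE1 = 0.0756, giving Φ(0.897) = 81.5%. A simplified Obuchowski variance gives 81.6%. Simulation gives 83.1% for a Wald test with DeLong's variance and 80.7% for a Mann-Whitney z-test.

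**Group sizes and drop-out.** 0.70 × 41 = 28.7, so 29/12 to the nearest patient; 28/41 = 68.3%. 41/0.9 = 45.6, so 46 strictly. 45 × 0.9 = 40.5. The stated 45 is consistent with 41 × 1.10 = 45.1.

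**Effect on power, same binormal formula throughout**

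| Responders / non-responders | Basis | SE0 | SE1 | Power |
|---|---|---|---|---|
| 28 / 13 | as stated | 0.0947 | 0.0782 | 82.9% |
| 28.7 / 12.3 | 70% of 41, unrounded | 0.0961 | 0.0794 | 81.6% |
| 28.35 / 12.15 | 70% of 40.5 | 0.0967 | 0.0799 | 81.1% |
| 29 / 12 | 70% of 41, rounded | 0.0968 | 0.0800 | 81.0% |
| 28 / 12 | 40 evaluable | 0.0973 | 0.0804 | 80.5% |

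The loss is 1.3 to 2.4 points. A figure below 80% at 29/12 or 28/12 appears on changing the formula as well: Hanley-McNeil gives Φ(0.829) = 79.6% at 29/12 and Φ(0.808) = 79.0% at 28/12. That mixes a rounding effect with a choice of method.

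**Where the primary test is stated**

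| Element | Place in section 6.0 |
|---|---|
| Primary endpoint, responder definition, ROC analysis | Objectives, Endpoints, and Study Design |
| Null, alternative, two-sided z-test, alpha | Sample Size and Power Calculation |
| ROC curves for both predictors, DeLong comparison | Analysis Plan |

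Read together, these define a test of the SUVmax-change AUC against 0.50 as the primary analysis. The comparison with size change concerns a secondary endpoint. The details left unwritten are the variance estimator, a confidence interval for the AUC and the comparator for DeLong.

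**The case for a change.** The strongest opposing argument concerns the test rather than the arithmetic. Without a named variance, the z-test could use DeLong's estimate, and simulation then puts the type I error against 0.50 at 6.3% to 6.8%; the rank-sum null variance gives 4.9%. This is a fair reason to prefer the null variance. But the plan does not say it will use DeLong's variance for this test, and either choice is a recognised form of the same comparison.

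The DeLong comparison of SUVmax with size change may well have low power: about 20% for AUCs of 0.76 and 0.66, and 41% for 0.76 and 0.60, at a correlation of 0.5. Those comparator AUCs and the correlation are assumptions with no source in the documents. The plan claims no power for that comparison, and its power sentence names the null of 0.50 explicitly.

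The split will also vary by chance. If the number of non-responders is binomial with probability 0.30, 13 or more arise only 46% of the time among 41 patients, and average power is 78.1% (Hanley-McNeil) to 79.7% (binormal). This is correct, but calculating at expected group sizes is ordinary practice. Likewise, taking non-responders as the positive group lowers Hanley-McNeil to 78.3% at 28/13, while the binormal figure stays at 82.9%. These points show how soft any single power figure is here; they do not show that the plan's figure is wrong.

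**Conclusion.** The concern does not call for a change. The 83% is reproducible from the numbers to which the plan ties it. The rounding points are correct, but each is a matter of about one patient, and with the formula held fixed power stays above 80%. In a self-described pilot with an estimated response rate, that alters neither the sample size decision nor the reading of the result.

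The powered test is present in section 6.0, one paragraph before the Analysis Plan. Leaving it unrepeated is a gap that a competent analyst fills from the same section. If the text is opened for another reason, the authors could restate the primary test and say what DeLong compares, but that is optional.

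This rests on the equal-variance binormal model, which the documents do not name but which matches their figure, and on reading section 6.0 as a whole.

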Primary objective: Evaluate metabolic response by 18F-fluciclovine PET qualitatively and semi-quantitatively with standardized uptake values (SUV) following standard systemic therapy at 22-28 weeks (+/- 4 weeks) and correlate the findings with size changes as defined by conventional imaging and PSA response.

Secondary objectives:

- 1. To correlate pelvic 18F-fluciclovine PET imaging findings with pathologic findings at radical prostatectomy and pelvic lymph node dissection to determine 18F-fluciclovine PET imaging sensitivity and specificity for pelvic lymph node cancer involvement.
- 2. To evaluate 18F-fluciclovine PET imaging response and its correlation with progression free survival (defined by PCWG2 criteria)
- 3. To determine if sites of progressive disease develop at the initial/prior site (diagnostic site) of metastases or in newly developed sites at the time of metastatic progression.
- 4. To evaluate metabolic response by 18F-fluciclovine PET semi-quantitatively with target to blood pool ratio (TBR) following SST at 22-28 weeks (+/- 4 weeks), and correlate the findings with size changes as defined by conventional imaging and PSA response.

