5.2 Reference standard

We will calculate tumor response by using RECIST 1.1 for visceral, bone and lymph node metastasis.²⁵ Primary tumor within the prostate gland will be assessed based on percent reduction in tumor size, changes in restricted diffusion and ADC value on mp pelvic MRI.²⁶⁻²⁸ In patient with available pathological specimen following prostatectomy and pelvic LN dissection, the pathologic response will be used to assess tumor response as well as identification of involved lymph nodes to assess for specificity and sensitivity of F18 Fluciclovine to detect occult lymph node involvement. Patients will be dichotomized by PSA measurement is taken at six months, PSA \leq 4 and PSA > 4.²⁹

Response assessment **Evaluation of Target lesions** Complete Response (CR) Disappearance of all target lesions. Any pathological lymph nodes (whether target or non-target) must have reduction in short axis to <10 mm. Partial Response (PR) At least a 30% decrease in the sum of diameters of target lesions, taking as reference the baseline sum diameters. At least 17% increase in median ADC value within the tumor on DWI MR images. Progressive Disease (PD): At least a 20% increase in the sum of diameters of target lesions, taking as reference the smallest sum on study (this includes the baseline sum if that is the smallest on study). In addition to the relative increase of 20%, the sum must also demonstrate an absolute increase of at least 5 mm. (Note: the appearance of one or more new lesions is also considered progression). Stable Disease (SD): Neither sufficient shrinkage to qualify for PR nor sufficient increase to qualify for PD, taking as reference the smallest sum diameters while on study. Evaluation of non-target lesions Complete Response (CR): Disappearance of all non-target lesions and normalization of tumor marker level. All lymph nodes must be non-pathological in size (<10mm short axis). Non-CR/Non-PD Persistence of one or more non-target lesion (s) and/or maintenance of tumor marker level above the normal limits. Progressive Disease (PD): Unequivocal progression (see comments below) of existing non-target lesions. (Note: the appearance of one or more new lesions is also considered progression).

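### Nodal sensitivity and specificity rest on operated men only; if the operated share differs by PET nodal result, the plain estimates are biased in opposite directions, and Section 6 has no check for this

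*Combined protocol and SAP*

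**What the plan says.** Secondary objective 1 (Section 3.0) compares pelvic PET findings with pathology at prostatectomy and node dissection, "to determine 18F-fluciclovine PET imaging sensitivity and specificity for pelvic lymph node cancer involvement". Section 5.2 limits the reference standard to some men: "In patient with available pathological specimen following prostatectomy and pelvic LN dissection". Surgery is not an eligibility criterion (Section 4.1). It is absent from the schema (Section 1.0) and the study calendar (Section 5.4), and no section gives a selection rule or an expected number of operations.

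The analysis plan in Section 6.0 says that sensitivity, specificity, PPV and NPV of dichotomized "PET CT imaging findings with pathologic findings will be estimated along with 95% confidence intervals". It says nothing about men without pathology.

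PET, in contrast, is planned for everyone: "All eligible patients will be imaged by 18F Fluciclovine PET CT before and after treatment". Under Section 5.1, uptake is "classified as lesions of the prostate, pelvic nodes, extrapelvic nodes, visceral, and bone lesions", so a pelvic nodal PET result should exist whether or not a man has surgery.

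**The concern.** Sensitivity and specificity condition on true nodal status, and here that status is known only in operated men. If PET-positive and PET-negative men reach surgery in different proportions, the mix of PET results in the verified group differs from the mix in the whole cohort. One of the two measures is then too high and the other too low (partial verification bias). PPV and NPV condition on the PET result, so they stay unbiased if surgery depends only on PET.

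What is at stake is the answer to secondary objective 1. A reader would take the figures as the accuracy of the tracer, although part of what they reflect could be the choice of men for surgery. The reported confidence intervals express sampling error and do not model this.

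**Working it through.** **The plan's own figures.** The documents give no expected nodal accuracy, number of operated men or precision for this objective. The 41 evaluable men come from the primary ROC calculation. Its stated 83% power reproduces: Φ((0.26 − 1.96·SE0)/SE1) gives 82.9% with the binormal variance and 81.5% with Hanley-McNeil. That calculation is not in dispute.

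**Assumed inputs (not in the documents).** Patient-level comparison with the post-treatment PET; 41 men, 20 PET-positive and 21 PET-negative; PPV 0.80; NPV 0.70.

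**True values.**
- TP = 20 × 0.80 = 16; FP = 4; TN = 21 × 0.70 = 14.7; FN = 6.3
- Sensitivity = 16/22.3 = 0.72
- Specificity = 14.7/18.7 = 0.79

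**Raw values in operated men.** With operated shares v+ (PET-positive) and v− (PET-negative):
- Raw sensitivity = v+·TP / (v+·TP + v−·FN)
- Raw specificity = v−·TN / (v−·TN + v+·FP)

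| v+ / v− | TP | FP | FN | TN | Raw sensitivity | Raw specificity |
|---|---|---|---|---|---|---|
| 40% / 40% | 6.4 | 1.6 | 2.52 | 5.88 | 0.72 | 0.79 |
| 30% / 50% | 4.8 | 1.2 | 3.15 | 7.35 | 0.60 | 0.86 |
| 25% / 60% | 4.0 | 1.0 | 3.78 | 8.82 | 0.51 | 0.90 |
| 20% / 70% | 3.2 | 0.8 | 4.41 | 10.29 | 0.42 | 0.93 |
| 60% / 25% | 9.6 | 2.4 | 1.575 | 3.675 | 0.86 | 0.60 |

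In every row PPV is 0.80 and NPV is 0.70.

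**Begg-Greenes estimate.** Take PPV and NPV from operated men, and the PET-positive fraction P+ (with P− = 1 − P+) from all men with a post-treatment PET:
- Sensitivity = PPV·P+ / [PPV·P+ + (1 − NPV)·P−]
- Specificity = NPV·P− / [NPV·P− + (1 − PPV)·P+]

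With P+ = 20/41, this returns 0.72 and 0.79 in every row, because selection depends only on PET.

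**Behavior at this size.** In 100,000 simulated trials of 41 men at 25%/60%, the root mean squared error for sensitivity falls from 0.28 (raw) to 0.14 (Begg-Greenes). For specificity it rises slightly, from 0.15 to 0.17. Under equal selection the correction loses nothing: 0.14 and 0.15, against 0.16 and 0.16 raw.

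**Sparse cells.** At 25%/60% only 20 × 0.25 = 5 PET-positive men are verified on average.
- The chance of no verified false positive is (1 − (20/41) × 0.25 × 0.20)^41 = 0.36. PPV is then 1, corrected specificity is 1, and a simple bootstrap shows no spread for it.
- At 10%/30% operated, the chance of no verified PET-positive man is (1 − (20/41) × 0.10)^41 = 0.13, and no correction can be computed.

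**If the key assumption fails.** Suppose that at 25%/60% node-positive men are operated on half as often as node-negative men with the same PET result. Counts become TP 2, FP 1, FN 1.89, TN 8.82, so PPV = 2/3 = 0.667 and NPV = 8.82/10.71 = 0.824.
- Corrected sensitivity = 13.33/(13.33 + 3.71) = 0.78
- Corrected specificity = 17.29/(17.29 + 6.67) = 0.72

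The true values are 0.72 and 0.79, so the corrected figures are off as well, though less than the raw 0.51 and 0.90.

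**The case against.** **Selection on imaging is not shown.** A reader might infer that surgery is likely to depend on residual nodal disease on PET or MRI. The documents do not support that. They do not say who is operated on, why, or whether PET results reach the treating team. Section 5.1 says "Blinded image interpretation will be made by radiologists and nuclear medicine physician", which concerns the readers and settles nothing about disclosure. The PET is listed as a research scan in Section 5.4. This objection stands, and the point is therefore conditional.

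**The population is already described.** Section 3.0 refers to pathology at surgery and Section 5.2 to men with a specimen, so a careful reader can see where the figures come from. That is partly right. But the objective is worded as a property of the imaging, and Section 6.0 neither labels the estimates as applying to operated men nor asks for the counts a reader would need to judge selection.

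**Imprecision is as large as the bias.** It is tempting to say that the planned intervals would miss the truth. In the 25%/60% illustration they would not. With counts rounded to 4/8 and 9/10, exact 95% intervals are 0.16–0.84 and 0.55–1.00, and both contain the assumed true values. What remains is that the intervals are centered in the wrong place.

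**The correction is fragile.** With about five verified PET-positive men it may not improve specificity, it can fail outright, and further stratification by MRI nodal status is not feasible. This also stands. It makes Begg-Greenes a sensitivity analysis and not a replacement.

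**It is one unpowered secondary objective in a pilot.** True. Section 5.10 foresees a multicenter application after the pilot studies but does not say that nodal accuracy will inform it.

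**Conclusion.** The concern holds in conditional form. Pathology is confined to operated men, selection for surgery is undescribed, and the planned estimates take no account of it. If operated shares differ by PET nodal result, sensitivity and specificity move in opposite directions. In the illustrations raw sensitivity runs from 0.42 to 0.86 against a true 0.72, and raw specificity from 0.60 to 0.93 against a true 0.79. Which way they move depends on which PET group is operated on more often. Equal shares produce no bias.

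These sizes rest on assumed PPV, NPV, PET-positive fraction and operated shares, none of which the documents supply. They also assume a patient-level comparison with the post-treatment PET, whereas the plan does not state the unit (patient or node) or which scan is compared with pathology. The documents do not establish that bias will occur. The primary ROC analysis and its sample size are unaffected. A change to the analysis text is still worthwhile, because the plan already collects the PET data that the check needs.

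**What to change.** In Section 6.0:

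1. State that the pathology comparison is per patient and uses the post-treatment PET nodal result.
2. Report the number of men operated on and not operated on, by PET nodal result.
3. Label raw sensitivity and specificity as applying to operated men.
4. Pre-specify Begg-Greenes estimates as a sensitivity analysis beside the raw values. Use the PET-positive fraction among all men with a post-treatment PET, and compute them only when both PET categories contain verified men.
5. Use intervals that remain valid when a cell is zero, for example exact or Bayesian limits for PPV and NPV carried through the formula, and not a simple bootstrap.
6. Do not stratify further by MRI nodal status; the numbers will not support it.

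The cost is a few lines of analysis text and a small extra table, with no added scans, visits or patients. The downside is that the corrected values will be imprecise, specificity may be no more accurate at this size, and the correction assumes that surgery is independent of true nodal status given the PET result. The report should say so.
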